6.3 Hospital Course Outcomes

Hospital Course outcomes that may be considered in analysis are:

- Proven NEC (*Binary, PH13, G.4, if PH13PNEC = 2 or 3.*)
- Spontaneous Intestinal perforation without proven NEC (SIP) (*Binary, PH13: G.5, PH13GAST, if PH13GAST = ‘Y’*)

⁵ Subcutaneous fat necrosis may occur after 108 hours.

- seizures after beginning of assigned treatment {Clinical Seizures} (Binary, PH13: D.1.b, D.1.c, D.1.d, D.1.e, taken from PH13SZAB, or PH13SZDM, or PH13SZRW, or PH13SZNT equal to 'Y')
- culture-positive bloodstream or infection of other normally sterile site at >3 days (Binary, PH13: E.1, E.2, PH13SEPT or PH13MENG needs to be 'Y')
- persistent pulmonary hypertension (PPHN) after start of intervention period (Binary, PH13: B.2, PH13PPHN)
- metabolic abnormalities after start of intervention period (Binary, PH13: I.1, I.2, I.3, I.4, I.5, I.6, I.7, PH13HYGL = 'Y' or PH13HYRG = 'Y' or PH13HYCA = 'Y' or PH13HYMA = 'Y' or PH13HYKA = 'Y' or PH13HYRK = 'Y' or PH13HYPH = 'Y')
- treatment with vasopressors and/or steroids after start of intervention period (Binary, PH13: C.7, PH13INOV)
- oliguria after start of intervention period (Binary, PH13: F.1, PH13OLIG)
- anuria after start of intervention period (Binary, PH13: F.2, PH13ANUR)
- liver dysfunction after start of intervention period (AST>200 IU and/or ALT>100 IU) (Binary, PH13: G.7, PH13EAST)
- liver dysfunction after start of intervention period (elevated direct bilirubin) (Binary, PH13: G.8, PH13EDBR)
- clinically diagnosed coagulopathy after start of intervention period (Binary, PH13: H.1, PH13DIC)
- days receiving oxygen/mechanical ventilation (Continuous, PH13: B.6, B.7, B.8, based on PH13DVEN and PH13DOXY, and PH13DCPA)
- Ventilation (Binary, if days receiving oxygen/mechanical ventilation > 0 then = yes)
- duration of NICU stay among survivors (Continuous, PH13: R.1, PH13DSDT (date of discharge) minus PH05: A.1.a, PH5BRTDT (birthdate))
- Bowel perforation (multi-level, = 'NEC' if PH13 G4 = 2, = 'NEC with Perforation' if PH13 G4 = 3, = 'SIP if PH13 G5 = 'Y')
- neurological injury by cranial ultrasound within 24 hours of enrollment, identified by local reader (Binary, PH12, see sub-section Analysis of Ultrasound, CT scan, MRI and encephalopathy outcomes under section 6.5.5.)
- Abnormal neurological examination at discharge
- Death prior to discharge
- Electrographic seizures (Binary, PH13: D.2.c = 'Y' or D.2.d='Y', and date/time D.2.b consistent with date occurring after intervention period)
- Anti-seizure medications at discharge (Binary, PH13: D.4 = 'Y')
- DNR order (Binary, PH13: P.2 = 'Y')
- DNR order and support withdrawn (Binary, PH13: P.2 = 'Y' and PH13 P.1.b.1, 2, 3, 4, or 5 = 'Y')

Note: The above listed safety outcomes will be summarized under the heading “during study intervention”, while the hospital course outcomes will be summarized under the heading “during hospital course”, which will be defined as the period between birth and death or discharge. See tables shell documents for more details.

6.4 Secondary Outcome

Table 3 of the MockTablesAppendix.docx document contains the secondary outcomes that will be summarized in the primary published paper. Secondary outcomes that may be considered during initial analysis will include but not necessarily limited to:

- death (*Binary, sources used to identify are listed in Section 6.1*)
- cause of death (withdrawal of support and reasons for such will be tracked) (*Multiple level discrete, PH13 PH13DCOD.*)
- disability in survivors (*Multi-level discrete, None/mild/moderate/Severe disability, derivations given in Section 6.1*)
- death or profound disability (assignment of lowest score on Bayley III because untestable due to degree of impairment) (*Binary, sources used to identify death are listed in Section 6.1, will need to use NF9a.nf9acsur variables to identify infants who had Bayley III cognitive score set to lowest score due to severe delay in development.*)
- survival with no disability (*Binary, no indication of death and disability assessment equal 'Normal' as calculated in Section 6.1*)
- death or severe disability (*Binary, indication of death and indication of severe disability assessment as calculated in Section 6.1*)
- moderate or severe disability among survivors (*Binary, use information regarding death and section 6.1 for calculation*)
- severe disability among survivors (*Binary, use information regarding death and section 6.1 for calculation*)
- moderate disability among survivors (*Binary, use information regarding death and section 6.1 for calculation*)
- profound disability among survivors (*Binary, use information regarding death and section 6.1 for calculation*)
- mild disability among survivors (*Binary, use information regarding death and section 6.1 for calculation*)
- no disability among survivors (*Binary, use information regarding death and section 6.1 for calculation*)
- Cerebral palsy (Any, Quadriplegic, Diplegic, Hemiplegic, Dystonic, Athetotic, Ataxic, Other, Disabling (moderate or severe), (*Binary, using information from PF05 C.9.a, C.9.b, C.9.c.*)
- a Bayley III language score < 70 (*Binary, among survivors, see section 6.1*)
- a Bayley III language score 70 - 84 (*Binary, among survivors, see section 6.1*)
- a Bayley III language score >= 85 (*Binary, among survivors, see section 6.1*)
- a Bayley III motor score < 70 (*Binary, among survivors, see section 6.1*)
- a Bayley III motor score 70 - 84 (*Binary, among survivors, see section 6.1*)
- a Bayley III motor score >= 85 (*Binary, among survivors, see section 6.1*)
- Head circumference < 10th percentile, among survivors (*Binary, based on PF05 follow-up form question A.3*)
- Weight < 10th percentile, among survivors (*Binary, based on PF05 follow-up form question A.1*)
- Length/height < 10th percentile, among survivors (*Binary, based on PH05 follow-up form questions*)
- each component of severe and moderate disability (among survivors):

- a Bayley III cognitive score < 70 (*Binary, see section 6.1*)
- a Bayley III cognitive score 70 - 84 (*Binary, see section 6.1*)
- a Bayley III cognitive score >= 85 (*Binary, see section 6.1*)
- Gross Motor Functional (GMFCS) Level of 3-5 (*Binary, see section 6.1*)
- blindness (visual acuity < 20/200 in the best eye as determined by an ophthalmologist) (*Binary, see section 6.1*)
- profound hearing loss (*Binary, see section 6.1*)
- a hearing deficit requiring amplification or cochlear implant to understand commands (*Binary, see section 6.1*)
- Seizures since discharge (*Binary, PF04 A.4 = 'Y'*)
- Abnormal neurological examination at discharge
- differences in MRI findings after cessation of cooling/control (*See subsection "Analysis of Ultrasound, CT scan, MRI and encephalopathy outcomes" under section 6.5.5 for more details*).

6.5 Analysis Methods

6.5.1 Statistical Methods

Patient accounting will be presented in a consort diagram. This diagram will include:

- Number of infants screened
 - Reasons for non-eligible
- Number of infants eligible
 - Reasons for non-consent
- Number of infants consented
- Number of infants randomized
- Number of infants randomized per group
 - Number withdrawn
 - Number lost-to-follow-up
- Number of infants who died
 - Before hospital discharge
 - Between hospital discharge and scheduled follow-up visit
- Number of infants with primary outcome per group

Baseline characteristics and outcomes will be descriptively summarized in the following manner:

Binary (yes/no 1/0 type) measures will be summarized by level with frequency out of the total non-missing values and percentage of total non-missing values. Percentages will be reported to one decimal place. For example: nn / NN (XX.X%)

Multiple level discrete measures will be tabulated with one row per level and with a row indicating how many observations had missing data. Percentages will be calculated as percent of all observations associated with a given treatment.

Continuous measures will be summarized by number of non-missing values, means and standard deviation [n: xx.x (xx.x)], or by median, minimum and maximum [n: xx.x, (xx.x, xx.x)] , or by median,

1st quartile, 3rd quartile [n: xx.x, (xx.x, xx.x)]. Standard deviations and continuous measures of mean, median, minimum, maximum, or quartiles will be reported to one decimal place.

Count measures that have more than 10 levels will be treated as continuous measures. Count measures that have 10 or fewer levels will be treated as multiple level discrete measures.

Statistical modeling and inference will be made using logistic models for binary outcomes, proportional odds models for ordinal outcomes, and negative binomial models for day and duration outcomes. All modeling will use Bayesian techniques to estimate the posterior distribution for all model parameters. Bayesian models will be fit using MCMC software such as PROC MCMC, JAGS, or Stan. The preferred software will be PROC MCMC, but if JAGS or Stan is used it will be accessed through R programming language-based packages such as rjags, rstan, rstanarm, or brms.

Model parameter estimates will be generated by fitting three MCMC chains. Each chain will involve at least 10,000 burn-in samples and at least 200,000 additional samples, which will be thinned by at least 5. More samples and more thinning will be done if necessary, to produce good sampling of the posterior. The final MCMC chains will have at least 120,000 useable samples to estimate the posterior distributions necessary for making inference about the treatment effects, (relative risk or outcome difference).

For binary outcomes, the outcome for the j^{th} infant from the i^{th} center will have the following form:

$$y_{ij} = \begin{cases} 0 & \text{survival without moderate / severe disability at 18-22 months corrected age} \\ 1 & \text{death or moderate / severe disability at 18-22 months corrected age} \end{cases}$$

The main covariates will have the form:

$$trt_{ij} = \begin{cases} 0 & \text{normothermia} \\ 1 & \text{whole body hypothermia} \end{cases}$$

$$enceph_{ij} = \begin{cases} 0 & \text{mild encephalopathy} \\ 1 & \text{moderate or severe encephalopathy} \end{cases}$$

The logistic model used for analysis of binary outcomes on the relative risk and risk difference scale will have the following form:

$$y_{ij} \sim \text{Bernoulli}[\pi_{ij}], \text{ where}$$

$$\text{logit}[\pi_{ij}] = \alpha_i + \theta_1 \cdot \text{enceph}_{ij} + \theta_2 \cdot \text{trt}_{ij}$$

β_1, β_2 will have priors as specified in Section 6.5.3

α_i will be the random intercepts due to center. Prior specified in Section 6.5.3.

The prior for the random center effects will be Normal centered at 0, and the hyperprior for the standard deviation of the random center effect will be specified in Section 6.5.3. Any baseline covariates that are added to the model (in sensitivity analyses to adjust for important unbalanced baseline covariates) will either be coded using 0/1 indicator variables, sets of indicator variables, or as centered continuous covariates. Priors for these other to-be-determined covariates are specified in Section 6.5.3. Post processing will be used to get posterior approximations of relative risk and risk differences due to treatment. The logistic model will be fit to the data, then for each infant, the model parameter chains will be used to estimate the within subject posterior relative risk and risk difference which will equal hypothermia divided by normothermia and hypothermia minus normothermia respectively. A within subject estimate of relative risk will be calculated by setting

the treatment variable value to hypothermia, estimating the probability of outcome for all infants, repeating the same process after setting the treatment variable to normothermia then dividing the two probabilities of outcome for all infants, hypothermia over normothermia. A within subject estimate of risk difference will be calculated by setting the treatment variable value to hypothermia, estimating the probability of outcome for all infants, repeating the same process after setting the treatment variable to normothermia then subtracting the two probabilities of outcome for all infants, hypothermia minus normothermia. Since the parameter chains will contain at least 120,000 samples, each infant will contribute at least 120,000 samples for the approximation of the within subject relative risk posterior and the within subject risk difference posterior. Using all samples of relative risk and risk differences from all infants to approximate the posteriors, the mean estimate of relative risk and risk difference will be calculated as well as, 95% credible intervals of mean relative risk and risk difference. Finally, posterior probabilities of benefit due to hypothermia from both relative risk and risk differences will be used as summary statistics. Differences in the relative risk and risk difference posteriors will be reflected upon to better understand the estimated treatment effect.

For count outcomes like days or duration, y_{ij} , the main covariates will have the form:

$$trt_{ij} = \begin{cases} 0 & \text{normothermia} \\ 1 & \text{whole body hypothermia} \end{cases}$$

$$enceph_{ij} = \begin{cases} 0 & \text{mild encephalopathy} \\ 1 & \text{moderate or severe encephalopathy} \end{cases}$$

The model used for analysis of day and duration outcomes will have the following form:

$$y_{ij} \sim \text{NegBinomial}[\vartheta_{ij}], \text{ where}$$

$$\ln(\vartheta_{ij}) = \alpha_i + \theta_1 \cdot enceph_{ij} + \theta_2 \cdot trt_{ij}$$

β_1, β_2 will have priors as specified in Section 6.5.4

α_i will be the random intercepts due to center. Prior specified in Section 6.5.4.

The prior for the random center effects will be Gaussian centered at 0, and the hyperprior for the standard deviation of the random center effect will be specified in Section 6.5.4. Any baseline covariates that are added to the model (in sensitivity analyses) will either be coded using 0/1 indicator variables, sets of indicator variables, or as centered continuous covariates. Priors for these other to-be-determined covariates are specified in Section 6.5.4.

The analysis of ordinal outcomes will use sets of logistic regression models as used for binary outcomes. One of the ordinal outcome levels will be designated as the reference level, and then logistic regression models will be fit to subsets of the data where one group of included data will be records that equal to reference level and the other group of included data will be records that equal one of the other outcome levels. For example, if an ordinal outcome has 3 levels, with level 3 designated as the reference level, then two logistic regression models will be fit:

- One model will use data from level 1 and level 3
- The second model will use data from level 2 and level 3

The prior for the random center effects will be Normal centered at 0, and the hyperprior for the standard deviation of the random center effect will be specified in Section 6.5.3. Any baseline covariates that are added to the model (in sensitivity analyses) will either be coded using 0/1 indicator variables, sets of indicator variables, or as centered continuous covariates. Priors for these other to-be-determined covariates are specified in Section 6.5.3.

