3.3 Randomization

After informed consent was obtained, qualifying infants were randomized by 6 hours of age to either hypothermia or the non-cooled control group. Randomization occurred 24 hours a day, 7 days a week through the Data Coordinating Center at RTI International, Research Triangle Park, NC. Infants were stratified by center and degree of NE (moderate versus severe). In the unlikely event of a multiple gestation qualifying for inclusion, all who qualified were randomized independently.

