5 TRIAL POPULATION

5.1 Screening population

All infants born at 33 0/7 to 35 6/7 weeks gestation and ≥ 1500 grams are screened for study entry if they are admitted to the NICU with an admitting diagnosis of acute perinatal asphyxia, neonatal depression, encephalopathy and/or fetal acidemia at less than 6 hours of age. All these infants at < 6 hours of age are evaluated by clinical and biochemical criteria and further assessed by neurological examination. Both inborn and outborn infants are evaluated. From this population, babies are screened for inclusion in the trial using the following eligibility criteria.

Eligibility

Inclusion criteria

Infants 33 0/7 to 35 6/7 weeks GA (best obstetrical estimate) and ≥ 1500 grams birth weight (to minimize potential difficulties placing esophageal probe) who meet clinical, biochemical and neurologic criteria for moderate to severe NE in this GA range at ≤ 6 hours age:

1) Biochemical:

Cord gas or if unavailable, blood gas within first hour of life with $\text{pH} \leq 7.00$ or base deficit (BD) ≥ 16 mEq/L, OR

2) Clinical in the absence of blood gas results or Clinical with more modest fetal acidemia (cord or 1st hour of life blood gas with a pH of 7.01-7.15 or BD > 10.0 to 15.9mEq/L):

a) Acute perinatal event (e.g., abruptio placenta, cord prolapse, uterine rupture, maternal cardiac or respiratory arrest, severe FHR abnormality such as variable or late decelerations,) AND

b) Requirement for positive pressure ventilation for apnea OR poor respiratory effort since birth for at least 10 minutes OR 10-minute Apgar score ≤ 5

AND

3) Neurologic:

Clinical Seizures OR modified Sarnat score with moderate or severe abnormalities in at least 3 of the 6 categories; at least one must be altered level of consciousness (lethargy or stupor/coma) as determined by a certified examiner.

All infants who meet criteria for potential inclusion should undergo standard neurologic exam as for infants ≥ 36 wks GA being considered for hypothermia, with findings recorded.

Criteria for exclusion in hypothermia trial

1) Receipt of paralytic agent or sufficient sedative or analgesic agent that is considered by the examiner to confound the qualifying neurologic exam

2) Etiology of NE not likely to be hypoxic-ischemic in origin

3) Major congenital anomaly that may confound outcome

4) Considered to be moribund and will not be receiving full intensive care

- 5) Equipment and/or appropriate staff not available

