5.3 Baseline Patient Characteristics

Baseline characteristics will be compared across treatment groups. Table 1 in the MockTablesAppendix.docx document lists out maternal and neonatal characteristics that will be summarized in the primary published paper. In addition to the variables indicated in Table 1 of the MockTablesAppendix.docx document, other baseline characteristics may be investigated internally by the Premie Hypothermia Subcommittee. For programming purposes, the following list contains an example list of infant and maternal characteristics that will or may be investigated as well as dataset and variable names needed to locate the characteristics in the clinical database:

- Infant baseline characteristics (*Variable Type, Form, Variable name in clinical database*)
 - Birth year (*Multiple level discrete, PH05: A.1.a, PH5BRTDT*)
 - GA (*Multiple level discrete – at level of weeks, PH05: A.7.a, PH5GESTW*)
 - Sex (*Binary, PH05: A.8, PH5SEX*)
 - Birthweight (grams) (*Continuous, PH05: A.4, PH5BRTWT*)
 - Length (cm) (*Continuous, PH05: A.5, PH5BRTLN*)
 - Head circumference (cm) (*Continuous, PH05: A.6, PH5HCIRC*)
 - Seizures (*Binary, PH02: C.1, PH2SIEZ*)
 - Level of Encephalopathy (*Binary, PH02: G.4, PH2LECEP*)
 - Inborn/outborn status (*Binary, PH05: A.2, PH5OUTBN*)
 - 1-minute Apgar scores (*Continuous, PH05: A.3.a, PH5APG1*)

- 5-minute Apgar scores (*Continuous, PH05: A.3.b, PH5APG5*)
- Received resuscitation at delivery (*Binary, PH05: B.1-B.5, PH5OXYG / PH5BAGM / PH5CHCOM / PH5INTUB / PH5DRUGS. any equal to 'Y'*)
 - Types of resuscitation (*Multiple level discrete or individual binary, use PH05: B.1-B.5, PH5OXYG / PH5BAGM / PH5CHCOM / PH5INTUB / PH5DRUGS.*)
- Received resuscitation at 10 minutes (*Binary, PH05: C.1-C.5, PH5OXY10 / PH5BAG10 / PH5CHE10 / PH5INT10 / PH5DRG10. Any equal to 'Y'*)
 - Types of resuscitation (*Multiple level discrete or individual binary, use PH05: C.1-C.5, PH5OXY10 / PH5BAG10 / PH5CHE10 / PH5INT10 / PH5DRG10.*)

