6.5.2 Covariates

All regression models will adjust for:

- level of encephalopathy at randomization and
- center (as a random effect).

The planned number of enrolling centers is 18, and center will be included in the linear component of the model as an additive random effect.

In addition to adjusting for level of encephalopathy and center as a random effect, sensitivity analyses will be completed by selecting baseline covariates that differ across the two treatments. These covariates will be selected from those covariates listed in section 5.3.

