6.5.7 Sensitivity Analysis

In addition to adjusting for level of encephalopathy and center as a random effect, sensitivity analyses may be completed, at the discretion of the Preemie Hypothermia subcommittee, by selecting baseline covariates that differ across the two treatments. These covariates will be selected from those covariates listed in section 5.3. This analysis will only be completed for the primary outcome (death or moderate to severe disability at 18-22 months corrected age) and Death. These sensitivity analyses will be based on the FAS population.

In addition to the FAS population-based analysis, exploratory PP analyses may be done using the PP population on the primary or secondary outcomes at the discretion of the Preemie Hypothermia subcommittee, if the FAS analysis of the primary or secondary outcome results in any clinically notable findings.

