6.5.8 Subgroup Analysis

The primary outcome will be reanalyzed for subgroup exploratory analyses. These analyses will be completed using the FAS population. These subgroup analyses will utilize interactions within the risk difference model defined in section 6.5.1 to study treatment heterogeneity and to estimate effects within subgroups when the treatment heterogeneity is clinically important. In each case, the subgroup variable will be added to the model, if not already in the model, along with the interaction between the subgroup variable and the treatment variable. These subgroup analyses will use modified versions of the models that included potentially important covariates and described in sections 6.5.1 and 6.5.2. Only the neutral priors will be considered in these analyses, and the priors for the interaction terms will be the same priors applied to the treatment groups as described in sections 6.5.3 and 6.5.4. In these models with interaction terms, effect coding will be used for treatment and level of encephalopathy instead of reference cell coding.

Reporting of subgroup analyses will include summary statistics from the Posterior distribution of the treatment effect within each level of the subgroup as well as generation of forest plots and posterior plots when deemed useful by the Preemie Hypothermia subcommittee. In addition to estimation of Posterior treatment effects within each level of the subgroup, summary posterior statistics of differences /ratios of treatment effects from all possible combinations of subgroup level pairs will be estimated (possible calculations here will be: differences in differences or ratio of ratios, since they will represent or be functions of effects that make up the interaction term(s) and other combinations not used to create interaction terms in the model given model parameterization). Summary posterior statistics will include medians, 95% credible intervals, and posterior probabilities of benefit.

The subgroups that will be considered are:

- Sex
- Center, if model estimation will allow it
- Race, provided we have sufficient diversity in the study population. At least two levels making up at least 20% each, and at least three levels represented.
- GA (3 levels: 33, 34, and 35 weeks)
- Infants who qualified on seizures alone vs. not (2 levels)
- Infants who had a baseline temperature < 36.5 °C vs. not (2 levels)
- Infants who had a baseline temperature < 35.0 °C vs. not (2 levels)

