- Infants who overshot the target and experienced esophageal temperatures < 32.0° C vs. not (an analysis using only babies in the cooling arm) (2 levels)
- Infants who had an abnormal cranial ultrasound after start of intervention but prior to final status will be compared to those who did not (2 levels).
- degree of NE (moderate versus severe)

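### The encephalopathy covariate in SAP 6.5.1 is coded mild versus moderate-or-severe, so it is constant in this trial and the main models do not adjust for the severity stratum

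*SAP*

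**What the plan says.** Section 6.5.1 gives each main model a center random intercept, an encephalopathy term and a treatment term. The encephalopathy indicator is defined as "0 & \text{mild encephalopathy} \\ 1 & \text{moderate or severe encephalopathy". The definition appears twice, once for binary outcomes and once for day and duration outcomes. Ordinal outcomes use sets of the same logistic models and so inherit it.

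Four other places describe the same factor differently:

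- 5.1 admits only infants "who meet clinical, biochemical and neurologic criteria for moderate to severe NE in this GA range".
- 3.3: "Infants were stratified by center and degree of NE (moderate versus severe".
- 6.5.2 says every regression model will adjust for "level of encephalopathy at randomization".
- 6.5.8 lists the subgroup as "degree of NE (moderate versus severe".

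The baseline list in 5.3 holds a suitable variable, "Level of Encephalopathy (*Binary, PH02: G.4, PH2LECEP", but does not state its two levels.

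**The concern.** The trial has no mild stratum, so the printed indicator takes one value. A constant covariate cannot adjust for anything. The stratification factor that 6.5.2 says is in every model is therefore absent from the primary, secondary, safety, count and ordinal analyses as specified.

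A programmer must either follow the formula and lose the stratum or depart from the printed definition of the primary model. If the formula is followed, results could be reported as adjusted for encephalopathy when they are not. The main outputs are posterior probabilities of benefit, and these would carry any chance imbalance in severe cases uncorrected. Some imbalance is possible despite stratification: 168 infants spread over 18 planned centers and two severity levels make small strata, and the full analysis set in 4.3 keeps only infants with an ascertained outcome.

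**Working it through.** **1. Rank.** Take N = 168, 84 per arm, and columns for intercept, encephalopathy and treatment. As printed, the encephalopathy column is all ones and the matrix has rank 2 of 3. Coded moderate/severe, it has rank 3 of 3.

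**2. What the priors do.** Section 6.5.3 puts Normal(0, 1) on both the intercept and the encephalopathy term. With a constant covariate the data inform only their sum. The difference keeps its prior variance of 1 + 1 = 2. If V is the posterior variance of the sum:

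- SD of the encephalopathy coefficient = √((V + 2)/4)
- correlation with the intercept = (V − 2)/(V + 2)

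Fits with the 6.5.3 priors and no center effect gave an SD of about 0.716. Then V = 4 × 0.716² − 2 = 0.051, and the implied correlation is −1.949/2.051 = −0.95, which is the fitted value. The SD is almost the no-information limit 1/√2 = 0.71. The priors alone divide the sum between the two terms, and moderate and severe infants in the same center and arm receive the same predicted risk.

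**3. Assumptions needed for size.** The SAP gives no risk by severity, no severe share and no block size. Assumed: 20–30% severe; control risks (moderate/severe) of 0.6/0.95, 0.6/0.90, 0.3/0.80, 0.5/0.85 and 0.65/0.85; permuted blocks of 2 or 4 within center and severity; 18 centers; n = 168; neutral prior Normal(0, 0.7072) on the treatment log odds ratio. Posteriors are Laplace approximations without the center effect.

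**4. Arms balanced on severity.** Posterior SD of the marginal log relative risk is 1–12% larger as printed. The probability that the relative risk is below 1 moves by at most about 0.04. The interval from pooling infant-level relative risks (6.5.1) is narrower as printed, with a width ratio of 0.81–0.97; all infants in an arm and center share one risk, so variation by severity disappears.

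**5. Simulated trials (1,500 per scenario).**

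| Quantity | Result |
|---|---|
| SD of the arm difference in percent severe | 2.8–3.8 points |
| Imbalance of 5 points or more | 8% of trials (blocks of 2), 16–20% (blocks of 4) |
| Mean shift in Pr(RR<1) | −0.03 to +0.01 |
| 95th percentile of absolute shift, true RR 0.7 | 0.01–0.10 |
| 95th percentile of absolute shift, true RR 1.0 | 0.05–0.14 |
| Codings on opposite sides of 0.80 | 0.1–6% of trials |

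The 0.80 mark is the posterior probability used in 3.4. With no interaction in the model, Pr(RR<1) equals the probability that the treatment log odds ratio is below 0, so these shifts do not depend on how infant-level ratios are pooled.

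**6. A 5-point imbalance by hand.** With 5 points more severe in the hypothermia arm, the crude relative risk is the true one times 1 + 0.05 × (severe risk − moderate risk)/(control-arm risk).

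- Risks 0.6/0.90, 20% severe overall: control-arm risk = 0.825 × 0.6 + 0.175 × 0.9 = 0.6525. Crude RR = 0.7 × (1 + 0.05 × 0.3/0.6525) = 0.716.
- Risks 0.3/0.80, 20% severe overall: control-arm risk = 0.825 × 0.3 + 0.175 × 0.8 = 0.3875. Crude RR = 0.7 × (1 + 0.05 × 0.5/0.3875) = 0.745.

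In the Bayesian fits over all scenarios the estimate is 0.757–0.781 as printed and 0.743–0.753 corrected. Both exceed 0.70 because the neutral prior pulls the effect toward 1; the gap between them is the cost of the coding.

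**The case against.** **The intent is recoverable.** Sections 3.3, 5.3, 6.5.2 and 6.5.8 together point to moderate versus severe, and a covariate equal to 1 throughout would probably be noticed at the first run. This is fair: it is a wrong level definition, not a decision to drop the stratifier. But the definition is printed twice, and no section gives a moderate/severe coding for the main models.

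**Other analyses cover the gap.** Sections 6.5.2 and 6.5.5 say covariate-adjusted sensitivity analyses will be done, and 6.5.5 allows adjustment in secondary analyses. However, 6.5.5 refers to 6.5.7 for the details, and there "sensitivity analyses may be completed, at the discretion of the Preemie Hypothermia subcommittee", for the primary outcome and death only. The severity subgroup is exploratory. Its rule that "the subgroup variable will be added to the model, if not already in the model" creates a further trap: if the printed indicator counts as already present, its interaction with treatment is aliased with treatment.

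**The upper ends of the size are unrealistic.** This stands in part. Risks of 0.3/0.80 give an overall control risk of 0.8 × 0.3 + 0.2 × 0.8 = 40% to 0.7 × 0.3 + 0.3 × 0.8 = 45%, whereas 3.4 cites 62% in the earlier trial and expects at least 70%. A separate run of 600 trials per scenario found the extremes only there. In the three scenarios with control risk 66–71% (0.6/0.95, 0.6/0.90, 0.65/0.85):

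- The SD ratio was 1.01–1.06.
- With balanced arms, the probability of benefit moved by at most about 0.015.
- At RR 0.7, the 95th-percentile shift was 0.01–0.03, with under 2% discordant at 0.80.
- At RR 1.0, the shift was 0.05–0.10, with 1–4% discordant.
- A 5-point imbalance gave about 0.76 as printed against 0.75 corrected.

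**An infant could be coded 0.** One randomized in error, or one qualifying on seizures alone and graded mild, might be. That would not supply a moderate/severe contrast.

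**Conclusion.** The concern holds: the covariate definition is wrong as written. As printed, the main models adjust for center but not for degree of encephalopathy, contrary to 6.5.2. This conclusion rests only on the SAP's eligibility, stratification and model definitions and needs no numerical assumption.

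The expected effect on the result is small. At control risks near those in 3.4, it is a few hundredths at most in the probability of benefit when the true RR is 0.7, and up to about 0.10 at the 95th percentile when there is no effect. It is larger only if control risk is much lower and severity strongly prognostic. All of these sizes depend on assumed severity shares, risks and block sizes, and on leaving out the center effect. The point should be fixed because it sits in the definition of the primary model and contradicts the stated adjustment, not because a large distortion is expected.

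**What to change.** In both formulas of 6.5.1, define the encephalopathy indicator as 0 = moderate and 1 = severe at randomization. Name the source variable already listed in 5.3 (form PH02, item G.4, PH2LECEP) and state its levels. Section 4.2 lists use of the wrong stratification variables as a possible deviation, so add a clause saying which value is used when the recorded level and the randomization stratum differ; the wording of 6.5.2 already points to the level at randomization.

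The cost is a one-line correction in two places plus that clause. The variable is already collected, and neither the design nor the priors need to change.
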